9.2 Guidelines for Evaluation of Measurable Disease

All measurements should be taken and recorded in metric notation using a ruler or calipers. All baseline evaluations should be performed as closely as possible to the beginning of treatment and never more than 4 weeks before the beginning of the treatment.

Note: Tumor lesions that are situated in a previously irradiated area might or might not be considered measurable.

The same method of assessment and the same technique should be used to characterize each identified and reported lesion at baseline and during follow-up. Imaging-based evaluation is preferred to evaluation by clinical examination when both methods have been used to assess the antitumor effect of a treatment.

Clinical lesions. Clinical lesions will only be considered measurable when they are superficial (e.g., skin nodules and palpable lymph nodes). In the case of skin lesions, documentation by color photography, including a ruler to

estimate the size of the lesion, is recommended.

Chest x-ray. Lesions on chest x-ray are acceptable as measurable lesions when they are clearly defined and surrounded by aerated lung. However, CT is preferable.

Conventional CT and MRI. These techniques should be performed with cuts of 10 mm or less in slice thickness contiguously. Spiral CT should be performed using a 5 mm contiguous reconstruction algorithm. This applies to tumors of the chest, abdomen, and pelvis. Head and neck tumors and those of extremities usually require specific protocols.

Ultrasound (US). When the primary endpoint of the study is objective response evaluation, US should not be used to measure tumor lesions. It is, however, a possible alternative to clinical measurements of superficial palpable lymph nodes, subcutaneous lesions, and thyroid nodules. US might also be useful to confirm the complete disappearance of superficial lesions usually assessed by clinical examination.

Endoscopy, Laparoscopy. The utilization of these techniques for objective tumor evaluation has not yet been fully and widely validated. Their uses in this specific context require sophisticated equipment and a high level of expertise that may only be available in some centers. Therefore, the utilization of such techniques for objective tumor response should be restricted to validation purposes in reference centers. However, such techniques can be useful to confirm complete pathological response when biopsies are obtained.

Tumor markers. Tumor markers alone cannot be used to assess response. If markers are initially above the upper normal limit, they must normalize for a patient to be considered in complete clinical response. Specific additional criteria for standardized usage of prostate-specific antigen (PSA) and CA-125 response in support of clinical trials are being developed.

Cytology, Histology. These techniques can be used to differentiate between partial responses (PR) and complete responses (CR) in rare cases (e.g., residual lesions in tumor types such as germ cell tumors, where known residual benign tumors can remain).

The cytological confirmation of the neoplastic origin of any effusion that appears or worsens during treatment when the measurable tumor has met criteria for response or stable disease is mandatory to differentiate between response or stable disease (an effusion may be a side effect of the treatment) and progressive disease.

9.3 Response Criteria

9.3.1 Evaluation of Target Lesions

Complete Response (CR): Disappearance of all target lesions

Partial Response (PR): At least a 30% decrease in the sum of the longest diameter (LD) of target lesions, taking as reference the baseline sum LD

Progressive Disease (PD): At least a 20% increase in the sum of the LD of target lesions, taking as reference the smallest sum LD recorded since the treatment started or the appearance of one or more new lesions

Stable Disease (SD): Neither sufficient shrinkage to qualify for PR nor sufficient increase to qualify for PD, taking as reference the smallest sum LD since the treatment started

9.3.2 Evaluation of Non-target Lesions

Complete Response (CR): Disappearance of all non-target lesions and normalization of tumor marker level

Incomplete Response/
Stable Disease (SD): Persistence of one or more non-target lesion(s) or/and maintenance of tumor marker level above the normal limits

Progressive Disease (PD): Appearance of one or more new lesions and/or unequivocal progression of existing non-target lesions

Although a clear progression of “non-target” lesions only is exceptional, in such circumstances, the opinion of the treating physician should prevail, and the progression status should be confirmed at a later time by the review panel (or study chair).

Note: If tumor markers are initially above the upper normal limit, they must normalize for a patient to be considered in complete clinical response.

9.3.3 Evaluation of Best Overall Response

The best overall response is the best response recorded from the start of the treatment until disease progression/recurrence (taking as

reference for progressive disease the smallest measurements recorded since the treatment started). The patient's best response assignment will depend on the achievement of both measurement and confirmation criteria (see section 9.3.1 and 9.4.1).

Target Lesions	Non-target Lesions	New Lesions	Overall Response
CR	CR	No	CR
CR	Incomplete response/SD	No	PR
PR	Non-PD	No	PR
SD	Non-PD	No	SD
PD	Any	Yes or No	PD
Any	PD	Yes or No	PD
Any	Any	Yes	PD

Note:

- Patients with a global deterioration of health status requiring discontinuation of treatment without objective evidence of disease progression at that time should be classified as having “symptomatic deterioration.” Every effort should be made to document the objective progression, even after discontinuation of treatment.
- In some circumstances, it may be difficult to distinguish residual disease from normal tissue. When the evaluation of complete response depends on this determination, it is recommended that the residual lesion be investigated (fine needle aspirate/biopsy) before confirming the complete response status.

9.4 Confirmatory Measurement/Duration of Response

9.4.1 Confirmation

To be assigned a status of PR or CR, changes in tumor measurements must be confirmed by repeat assessments that should be performed at a minimum of 4 weeks after the criteria for response are first met. In the case of SD, confirmatory scans must have met the SD criteria at least once at a minimum interval of 4 weeks (see section 9.3.3).

9.4.2 Duration of Overall Response

The duration of overall response is measured from the time measurement criteria are met for CR or PR (whichever is first recorded) until the first date that recurrent or progressive disease is objectively documented (taking as reference for progressive disease the smallest measurements recorded since the treatment started).

The duration of overall CR is measured from the time measurement criteria are first met for CR until the first date that recurrent disease is objectively documented.

9.4.3 Duration of Stable Disease

Stable disease is measured from the start of the treatment until the criteria for progression are met, taking as reference the smallest measurements recorded since the treatment started.

9.5 Evaluation of response in patients with CNS disease (cohort B)

In addition to evaluation of response using RECIST criteria, additional analyses will be performed on patients with CNS disease enrolled in cohort B. More specifically, contrast-enhanced MRI or CT scans and neurological examinations will be used to determine the response to therapy.

The following modified definitions of response will be used in the additional analyses:

- Complete Response: Complete disappearance of all tumor on MRI/CT scan, off all glucocorticoids with a stable or improving neurological examination for a minimum of 4 weeks.
- Partial Response: Greater than or equal to 50% reduction in tumor size on MRI/CT scan, on a stable or decreasing dose of glucocorticoids, with a stable or improving neurological examination for a minimum of 4 weeks.
- Progressive Disease: Progressive neurological abnormalities not explained by causes unrelated to tumor progression (e.g. anticonvulsant or corticosteroid toxicity, electrolyte abnormalities, hyperglycemia, etc.) or a greater than 25% increase in the size of the tumor by MRI/CT scan. If neurological status deteriorates, on a stable or
- increasing dose of steroids, or if new lesions appear on serial MRI/CT, further study treatment will be discontinued.

- Stable Disease: A patient whose clinical status and MRI/CT scan do not meet the criteria for *Complete Response*, *Partial Response* or *Progressive Disease*.

10. ADVERSE EVENTS: LIST AND REPORTING REQUIREMENTS

This protocol will adhere to the policies of the Case Comprehensive Cancer Center Data and Safety Monitoring Plan in accordance with NCI regulations.

Adverse event (AE) monitoring and reporting is a routine part of every clinical trial. The following list of AEs (*Section 10.1*) and the characteristics of an observed AE (*Section 10.2*) will determine whether the event requires expedited reporting **in addition** to routine reporting.

10.1 Comprehensive Adverse Events and Potential Risks Lists

10.1.1 CAEPR

The Comprehensive Adverse Event and Potential Risks list (CAEPR) provides a single, complete list of reported and/or potential adverse events (AE) associated with an agent using a uniform presentation of events by body system.

In addition to the comprehensive list, a subset, the Agent Specific Adverse Event List (ASAEL), appears in a separate column and is identified with **bold** and *italicized* text. This subset of AEs (the ASAEL) contains events that are considered ‘expected’ for expedited reporting purposes only.

10.1.1.1 Comprehensive Adverse Events and Potential Risks List (CAEPR) for Methoxyamine

The Comprehensive Adverse Event and Potential Risks list (CAEPR) was developed to provide a single, complete list of reported and/or potential adverse events associated with an agent using a uniform presentation of events by body system. The table below identifies reported adverse events (AEs) that may be expected to occur with Methoxyamine and/or Temozolamide. The subset of AEs that is used to guide expedited reporting requirements [i.e., the Agent Specific Adverse Event List (ASAEL)], as presented in the right hand column, is identified with **bold** and *italic* text. This subset contains events that are considered expected and may not need to be reported via expedited AE reporting.

Category (Body System)	Adverse Events with Possible Relationship to Methoxyamine (CTCAE v3.0 Term)			“Expected” Adverse Events (see above)
	Likely	Less Likely	Rare but Serious	

	(> 20%)	(≤ 20%)	(< 3%)	
ALLERGY/IMMUNOLOGY			Allergic reaction	
BLOOD AND LYMPHATIC SYSTEM DISORDERS			Febrile neutropenia	
CONSTITUTIONAL SYMPTOMS				
DERMATOLOGY/SKIN				
ENDOCRINE				
GASTROINTESTINAL				
HEMORRHAGE/BLEEDING				
HEPATOBILIARY/PANCREAS				
INFECTION				
METABOLIC/LABORATORY				
NEUROLOGY			hallucinations	
PAIN				
PULMONARY/UPPER RESPIRATORY				
VASCULAR				

10.2 Adverse Event Characteristics

- **CTCAE term (AE description) and grade:** The descriptions and grading scales found in the revised NCI Common Terminology Criteria for Adverse Events (CTCAE) version 3.0 will be utilized for AE reporting. All appropriate treatment areas should have access to a copy of the CTCAE version 3.0. A copy of the CTCAE version 3.0 can be downloaded from the CTEP web site (<http://ctep.cancer.gov>).
- **‘Expectedness’:** AEs can be ‘Unexpected’ or ‘Expected’ (*see Section X.1 above*) for expedited reporting purposes only. ‘Expected’ AEs (the ASAEL) are ***bold and italicized*** in the CAEPR (*Section X.1.1*).
- **Attribution of the AE:**
 - Definite – The AE is *clearly related* to the study treatment.
 - Probable – The AE is *likely related* to the study treatment.
 - Possible – The AE *may be related* to the study treatment.
 - Unlikely – The AE is *doubtfully related* to the study treatment.
 - Unrelated – The AE is *clearly NOT related* to the study treatment.

10.3 SERIOUS ADVERSE EVENT (SAE) REPORTING

All adverse clinical experiences, whether observed by the investigator or reported by the patient, must be recorded, with details about the duration and intensity of each episode, the action taken with respect to the study agent(s), and the patient's outcome. The investigator must evaluate each adverse experience for its relationship to the study agents and for its seriousness.

The investigator must evaluate all abnormal laboratory results for their clinical significance. If any abnormal laboratory result is considered clinically significant, the investigator must provide details about the action taken with respect to the combination of drugs and about the patient's outcome.

Adverse events will use the descriptions and grading scales found in the revised NCI Common Toxicity Criteria (CTC), version 3.0.

Severity Ratings

The investigator will evaluate the severity of each adverse experience using the following definitions:

- Mild-noticeable to the patient, does not interfere with the patient's daily activities, usually does not require additional therapy, dose reduction, or discontinuation of the study drug.
- Moderate-interferes with the patient's daily activities, possibly requires additional therapy, but does not require discontinuation of study drug.
- Severe-severely limits the patient's daily activities and may require discontinuation of the study drug.

Serious, Life-threatening, or Unexpected Adverse Experience (21 CFR 314.80)

- A “serious” adverse event (experience) or reaction is any untoward medical occurrence that at any dose: results in death, is life threatening, results in persistent, significant and/or permanent disability/incapacity, requires inpatient hospitalization or prolongation of existing hospitalization, or is a congenital anomaly/birth defect. A “life-threatening” adverse experience places the patient at immediate risk of death in the judgment of the investigator.
- The definition of serious adverse event (experience) also includes *important medical event*. Medical and scientific judgment should be exercised in deciding whether expedited reporting is appropriate in other situations, such as important medical events that may not be immediately life-threatening or result in death or hospitalization but may jeopardize the patient or may require intervention to prevent one of the other outcomes listed in the definition above. These should also usually be considered serious. Examples of such events are intensive treatment in an emergency room or at home for allergic

bronchospasm; blood dyscrasias or convulsions that do not result in hospitalization; or development of drug dependency or drug abuse.

- An “unexpected” adverse experience is one not identified in nature, severity, or frequency in the Investigator’s Brochure or the product package insert for the study drug.

Relationship to Study Drug

- Probably Related-the experience occurs within a reasonable time period following drug administration or follows a known response for the drug and cannot be reasonably explained by known patient characteristics (including use of concomitant medications). The definition of “related” being that there is a reasonable possibility that the drug caused the adverse experience.
- Unknown Relationship-the etiology of the experience is not known and the experience does not occur within a reasonable time period following drug administration and does not follow a known response pattern for the drug.
- Definitely Not Related-the experience is not known to be caused by the study drug.

Investigator Reporting Responsibilities

The conduct of the study will comply with all FDA safety reporting requirements.

All adverse experience reports must include the patient number, age, sex, weight, severity of reaction (mild, moderate, severe), relationship to study drug (probably related, unknown relationship, definitely not related), date and time of administration of test medications and all concomitant medications, and medical treatment provided. The investigator will record this information on FORM 3500 A (or Medwatch form) and will provide reports of adverse experiences on a regular basis during the study conduct. The investigator is responsible for evaluating all adverse events to determine whether criteria for “serious” and “unexpected” as defined above are present.

Adverse Drug Reaction Reporting

Toxicity will be scored using CTCAE Version 3.0 for toxicity and adverse event reporting. A copy of the CTCAE Version 3.0 can be downloaded from the CTEP homepage (<http://ctep.info.nih.gov>). All appropriate treatment areas have access to a copy of the CTCAE Version 3.0. All adverse clinical experiences, whether observed by the investigator or reported by the patient, must be recorded, with details about the duration and intensity of each episode, the action taken with respect to the test drug, and the patient's outcome. The investigator must evaluate each adverse experience for its relationship to the test drug and for its seriousness.

The investigator must appraise all abnormal laboratory results for their clinical significance. If any abnormal laboratory result is considered clinically significant,

the investigator must provide details about the action taken with respect to the test drug and about the patient's outcome.

Investigator Reporting to the FDA:

Adverse drug reactions should be reported promptly to the Food and Drug Administration (FDA) in writing by each investigator/physician engaged in clinical research if the type of effect is **Serious, Unlisted/unexpected event, and at least possibly associated to the drug** and has not previously been reported in the Investigators brochure, or reference safety information document, or literature. A clear description of the suspected reaction should be provided along with an assessment as to whether the event is drug or disease related.

The investigator/physician must also call the FDA as soon as an adverse reaction occurs. The phone number is [contact]. A recorder is available after hours. Report these reactions to the FDA within ten (10) working days both verbal and written.

The address of the Food and Drug Administration is:

FDA
Division of Oncology
HFD-150
[name]
[name]

The phone number of the FDA is [contact]. Please ask to speak with [name] in the Division of Oncology

10.4 DATA SAFETY AND MONITORING PLAN

This protocol will adhere to the policies of the Case Comprehensive Cancer Center Data and Safety Monitoring Plan in accordance with NCI regulations. The Data and Safety Toxicity Committee will review all serious adverse events and toxicity reports as well as annual reviews.

11.0 REGULATORY AND DATA REPORTING REQUIREMENTS

Data will also be collected using the Oncore database at the Case Comprehensive Cancer Center.

Initial Enrollment Forms – at time of enrollment

Patient History Form– within 2 weeks of enrollment

Lab Form – Weekly during treatment

Course Assessment Form – For each treatment cycle

Physical Assessment, Vital Signs and Toxicity Form – For each treatment cycle

Response Form – At the time response is assessed/confirmed

Off Treatment Form – When patient comes off treatment

Survival Form – Patients to be followed annually for survival

12. STATISTICAL CONSIDERATIONS

For cohort A, a maximum of 36 patients can theoretically participate on this study, based on 6 dose levels with a maximum of 6 patients at each dose level. However, given the fact that a 10-fold increase in MX is being tested in 6 consecutive dose escalation levels it is highly unlikely that the maximum number of patients will need to be enrolled at each level.

For cohort B, a maximum of 42 patients can theoretically participate on this study, based on 7 dose levels with a maximum of 6 patients at each dose level. However, given the fact that a 1.5-fold increase in TMZ and a 10-fold increase in MX is being tested in 7 dose escalation levels it is highly unlikely that the maximum number of patients will need to be enrolled at each level.

The following table gives the probabilities of escalating under given true but unknown underlying rates of DLT:

True Underlying DLT Rate	0.1	0.2	0.3	0.4	0.5
Escalate to next full dose	0.91	0.71	0.49	0.32	0.17
Do not escalate; prior dose level is MTD	0.09	0.29	0.51	0.68	0.83

Thus, if the true underlying rate of DLT is 20%, there will be a 71% chance of escalating to next full dose and a 29% chance that the lower dose will be chosen as the MTD.

The baseline levels (at 0h) of AP sites and DNA strand breaks will be compared to the levels at various time points (i.e. 2h, 4h and 122h) after treatment by paired T-test or Wilcoxon rank sum test. The predictive value of PK parameters (e.g. AUC, C_{max}), levels of AP sites and levels of DNA strand breaks on clinical response and grade 3/4 toxicity will be examined by logistic regression after adjusting the dose level; their predictive value on time to event outcomes, such as disease progression free survival, will be tested using (extended) Cox model after controlling other factors including dose level.

REFERENCES

1. L Liu, P Taverna, CM Whitacre, S Chatterjee, and SL Gerson. Pharmacologic disruption of base excision repair sensitizes mismatch repair-deficient and -proficient colon cancer cells to methylating agents. *Clin Cancer Res* 5:2908-2917, 1999.
2. L Liu, Y Nakatsuru, and SL Gerson. Base excision repair as a therapeutic target in colon cancer. *Clin Cancer Res* 8:2985-2991, 2002.
3. L Liu, JR Donze, and SL Gerson. Methoxyamine enhances antitumor efficacy of BCNU in colon tumor xenografts. *Proc Amer Assoc Cancer Res* 43:794 (#3938), 2002.

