4.1 Agent Administration

For all cycles, TMZ will be given orally for 5 days every 28 days. MX will be given as a single one-hour IV infusion every 28 days. Temozolomide will be administered within 5 minutes following the initiation of methoxamine.

Patients will be treated and monitored in the inpatient setting (Clinical Research Unit) during MX administration (on cycle 1 day 1). A physician will be onsite within the hospital in case an adverse event occurs.

Cohort A (eligible patients with no CNS disease)

DOSE-ESCALATION SCHEDULE		
Dose Level	Dose	
	TMZ (mg/m ² /day) x5days	MX (mg/m ²)
Level -1	100	15
Level 1	150	15
Level 2	150	30
Level 3	150	60
Level 4	150	90
Level 5	150	120
Level 6	150	150

Level 7	200	150
---------	-----	-----

Cohort B (eligible patients with CNS disease)

Dose Level	DOSE-ESCALATION SCHEDULE	
	Dose	
	TMZ (mg/m ² /day) x5days	MX (mg/m ²)
Level -1	75	15
Level 1	100	15
Level 2	150	15
Level 3	150	30
Level 4	150	60
Level 5	150	120
Level 6	150	150
Level 7	200	150

For each cohort, 3 patients will be entered sequentially to each dose level.

- If none of the 3 patients at a dose level experience dose limiting toxicity (DLT) during the first cycle, new patients may be entered at the next higher dose level.
- If 1/3 patients experience a DLT during the first cycle, up to 3 more patients will be treated at the same dose level. If the 1st patient in the expanded cohort (4th at the given DL), experiences no DLT, then the remaining 2 patients can start treatment without a necessary delay.
 - As of protocol v22, if 1/3 patients experience any DLT that is not of a CNS nature in Cohort B dose level 6, we will continue dose escalation to dose level 7 since we have already treated three subjects in Cohort A dose level 6 and seven subjects in Cohort A dose level 7, none of whom experienced non-CNS toxicities
- If 2 or more experience DLT during the first cycle, no further patients are started at that dose and the MTD is the highest dose level in which <2 (of 6) patients develop DLT.
- If the final dose level is deemed the MTD, 6 patients will be treated at this dose level even if a DLT has not been observed.

Select non-hematologic grade 3 or 4 or hematologic grade 4 drug-related toxicities (CTC version 3.0) occurring within the first 28 days of the study will be considered a DLT.

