Cohort A, Dose level 1: Two DLTs were observed in Dose Level 1 of Cohort A: grade 3 psychosis and grade 3 allergic reaction. Upon further review of the hypersensitivity reaction, it is believed that this was an idiosyncratic event, and further expansion of this

dose level is warranted. Dose level 1 of Cohort A will be expanded to 10 evaluable patients. Further dose escalation will occur only if less than 4 out of the 10 patients experience a DLT. Enrollment to subsequent dose levels will follow the rules outlined above.

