4.2 Definition of Dose-Limiting Toxicity (DLT) and Criteria for Dose Escalation

DLT in a given patient is defined as any grade III non-hematologic (thought to be MX related) or IV non-hematological toxicity or any grade IV anemia, neutropenia or thrombocytopenia lasting greater than 7 days, that is felt to be related to MX or the MX + TMZ drug combination occurring during the first cycle of treatment.

MTD (maximum tolerated dose) will be defined based on the toxicities observed during the first cycle of treatment

Definition of MTD: The MTD is defined as the highest dose tested in which none or only one patient experienced DLT attributable to the study drug combination, when at least six patients were treated at that dose and are evaluable for toxicity. The MTD is one dose level below the highest dose tested in which 2 or more patients experienced DLT attributable to the study drug. At least 6 patients will be treated at the MTD.

Management and dose modifications associated with the above adverse events are outlined in Section 5.

Special consideration is given to the evaluation of neurologic toxicity given the animal toxicity data and CNS involvement of a proportion of eligible patients.

Specifically:

- all patients will be evaluated by a staff Neurologist prior to initiation of treatment
- patients will undergo frequent (every 4-8 hours) neurologic checks by a CRU RN during the 1-day inpatient CRU stay on the first day of treatment.
- Patients will be evaluated by the covering Oncology clinician during the 1-day inpatient CRU stay on cycle 1.

A neurology consult will be obtained for any observed treatment-related neurologic toxicity \geq grade 2. For patients enrolled in cohort B (patients with CNS disease) with pre-existing neurologic toxicity cleared for participation by the neuro-oncology team, a neuro-oncology or neurology consult will be obtained for any observed treatment-related worsening in neurologic toxicities.

Dose escalation will proceed within each cohort according to the following scheme. DLT is defined above.

Number of Patients with DLT at a Given Dose Level	Escalation Decision Rule
0 out of 3	Enter 3 patients at the next dose level.
≥ 2	Dose escalation will be stopped. This dose level will be declared the maximally administered dose (highest dose administered). Three (3) additional patients will be entered at the next lowest dose level if only 3 patients were treated previously at that dose.

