1 out of 3	
Enter at least 3 more patients at this dose level.
 
 • If 0 of these 3 patients experience DLT, proceed to the next dose level. • If 1 or more of this group suffer DLT, then dose escalation is stopped, and this dose is declared the maximally administered dose. Three (3) additional patients will be entered at the next lowest dose level if only 3 patients were treated previously at that dose. 
 ◦ As of protocol v22, if 1/3 patients experience any DLT that is not of a CNS nature in Cohort B dose level 6, we will continue dose escalation to dose level 7 since we have already treated three subjects in Cohort A dose level 6 and seven subjects in Cohort A dose level 7, none of whom experienced non-CNS toxicities
≤ 1 out of 6 at highest dose level below the maximally administered dose	This is generally the recommended phase 2 dose. At least 6 patients must be entered at the recommended phase 2 dose.

Cohort A, Dose level 1: Dose level 1 of Cohort A will be expanded to 10 evaluable patients. Further dose escalation will occur only if less than 4 out of the 10 patients experience a DLT. Enrollment to subsequent dose levels will follow the rules outlined in Sec. 4.1.

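### The stated Cohort A maximum of 36 leaves out dose level 7 and the level 1 expansion; on Section 12's own cap of 6 at the other levels it should be 46 evaluable patients

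*Combined protocol and SAP*

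**What the plan says.** Section 12 opens with the Cohort A sample size: "For cohort A, a maximum of 36 patients can theoretically participate on this study, based on 6 dose levels". The multiplication behind it is explicit: "based on 6 dose levels with a maximum of 6 patients at each dose level". The section adds that the full number is unlikely to be needed, because "a 10-fold increase in MX is being tested in 6 consecutive dose escalation levels".

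The next paragraph of Section 12 gives Cohort B a maximum of 42, from seven levels of six.

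Other parts of the document describe Cohort A differently:

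- The Cohort A dose tables in the Schema and in Section 4.1 list level -1 and levels 1 to 7.
- Section 4.2 states: "Dose level 1 of Cohort A will be expanded to 10 evaluable patients". Section 4.1 carries the same expansion and adds the continuation rule: "Further dose escalation will occur only if less than 4 out of the 10 patients experience a DLT".
- Later levels return to the usual 3+3 pattern. After one DLT in the first three patients, a second group is entered, and "If 0 of these 3 patients experience DLT, proceed to the next dose level". When a level fails, "Three (3) additional patients will be entered at the next lowest dose level if only 3 patients were treated previously at that dose".
- The note added at protocol v22 reports that "we have already treated three subjects in Cohort A dose level 6 and seven subjects in Cohort A dose level 7".

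**The concern.** A theoretical maximum should bound what the escalation rules permit. If it is built from fewer levels than the schedule contains, and from a per-level cap that the protocol has lifted at one level, it is not a bound. In the text available, this is the only overall number given for Cohort A, so it is what an ethics committee, a monitoring committee or a reader would use to judge how many patients may be exposed.

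Section 12 is also inconsistent within itself. The two cohorts have schedules of the same length (level -1, then 1 to 7), yet adjacent paragraphs count seven levels for Cohort B and six for Cohort A.

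The stake is limited to the stated sample size. The probabilities of escalation in Section 12 are per-level quantities, and neither they nor the DLT and MTD definitions depend on the total.

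**Working it through.** **Inputs**

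| Input | Value | Source |
|---|---|---|
| Stated Cohort A maximum | 36, from 6 levels × 6 | Section 12 |
| Stated Cohort B maximum | 42, from 7 levels × 6 | Section 12 |
| Cohort A escalation levels | 7 (levels 1 to 7, plus level -1) | Schema; Section 4.1 tables |
| Level 1 size, Cohort A | 10 evaluable | Sections 4.1 and 4.2 |
| Cap at other levels | 6 | Section 12 |
| MX, Cohort A | 15 at level 1, 150 at levels 6 and 7 (mg/m²) | Schema; Section 4.1 tables |

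**Step 1: reproduce the plan's figures.** Cohort A: 6 × 6 = 36. Cohort B: 7 × 6 = 42. Both reproduce. The Cohort B figure shows the counting convention: levels 1 to 7 count and level -1 does not.

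**Step 2: where the six levels probably come from.** 150 / 15 = 10, so the tenfold MX range is complete at level 6. Level 7 leaves MX at 150 and raises only TMZ. A count tied to the MX range therefore stops at six and misses level 7.

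**Step 3: correct each input separately, then both.**

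- Seven levels only: 7 × 6 = 42 (6 more than stated).
- Level 1 expansion only: 10 + 5 × 6 = 40 (4 more).
- Both: 10 + 6 × 6 = 46 (10 more; 10 / 36 = 28%).

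**Step 4: can 46 be reached under the written rules?** Yes, with fewer than 4 DLTs among 10 at level 1, then one DLT in the first three and none in the next three at each of levels 2 to 6, then six at level 7. Total: 10 + 5 × 6 + 6 = 46. Counting every path (including the three patients added below a failed level when only three had been treated there) gives a maximum of 46 with seven levels and 40 with six. Level -1 does not raise this: it would be used only if level 1 failed, which gives at most 10 + 6 = 16.

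**Step 5: what the reported counts add.** Take 10 at level 1 as planned, with 3 at level 6 and 7 at level 7 as reported. Numbers at levels 2 to 5 are not given, so assume 3 to 6 at each.

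- As reported: from 10 + 4 × 3 + 3 + 7 = 32 to 10 + 4 × 6 + 3 + 7 = 44.
- If level 7 failed and three more were entered at level 6: from 10 + 4 × 3 + 6 + 7 = 35 to 10 + 4 × 6 + 6 + 7 = 47.

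These ranges mix treated and evaluable patients, and the second needs at least two DLTs at level 7, which the documents do not report. Both ranges straddle 36.

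**Step 6: both cohorts.** Section 12 gives no combined total. Adding its two figures gives 36 + 42 = 78; with the corrected Cohort A figure it is 46 + 42 = 88.

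**The case against.** The best argument on the other side is that 36 is not a miscalculation, that Section 12 itself calls it theoretical and unlikely to be reached, and that Cohort A has already enrolled at its top level, so a correction now mainly tidies the record. No overrun is shown. All of this is true. It limits the consequence, but it does not make 36 a bound on the current rules. Nor is the level 1 expansion a remote contingency: Section 4.1 directs it.

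A second argument is that 46 is not a hard ceiling either. Three points support this:

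- Seven patients are reported as treated at level 7. If the cap counts treated patients, it has already been passed there, and the count becomes 10 + 5 × 6 + 7 = 47.
- For the expansion after one DLT in three, Section 4.1 treats three further patients as the upper limit, while the decision table in Section 4.2 treats three as the minimum. A cap of six follows from Section 4.1 or from Section 12, but not from the Section 4.2 table.
- The 10 at level 1 are evaluable patients. If non-evaluable patients are replaced, enrolment would be higher.

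These points stand, and they are why 46 is given here only as conditional on Section 12's cap. All of them move the maximum further above 36; none brings it back.

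**Conclusion.** The concern holds. The stated Cohort A maximum is inconsistent with the dose schedule and with the level 1 rule. On Section 12's own cap of six at each of levels 2 to 7, counting evaluable patients and leaving out level -1, the maximum is 46. The plan's 36 is too low by 10 patients, or 28%.

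This is text that was not updated when the design changed, rather than an error in multiplication. Whether Cohort A actually passed 36 cannot be told from the documents. The defect is certain and inexpensive to correct, so it should be corrected, but it does not affect the escalation rules or the MTD.

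**What to change.** In the Cohort A paragraph of Section 12:

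- Change the number of dose levels from six to seven.
- State 10 evaluable patients at level 1 and a maximum of six at each of levels 2 to 7.
- Restate the maximum as 46 evaluable patients, excluding level -1.
- Say whether the figure counts treated or evaluable patients, and account for the seven reported as treated at level 7.

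Two related wordings should be reconciled in the same edit. The size of the expansion after one DLT in three differs between Section 4.1 (an upper limit of three) and the Section 4.2 table (a minimum of three); the cap of six, and so the 46, depends on how this is settled. Separately, and with no bearing on the Cohort A count, Section 12 describes the Cohort B TMZ range as a 1.5-fold rise, while the Cohort B table runs from 100 to 200, which is 2.0-fold.

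The cost is one text edit in Section 12 and one harmonised phrase in Sections 4.1 and 4.2. The stated maximum rises from 36 to 46. Correcting the count changes nothing in the design and calls for no additional patients; harmonising the expansion phrase only makes an existing rule read the same in both places.
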